11.3. Participant Accrual, Follow-up and Retention

Based on previous studies of influenza vaccination among children, the accrual of 100 total and 80 evaluable participants will take approximately 2 years (or 2 flu seasons). Participants lost to follow-up and/or discontinued early from the study will not be replaced. The study team will consider a participant “lost to follow-up” for this trial if he or she has missed 2 consecutive study visits and is unreachable after multiple contact attempts by study staff. However, every effort will be made to complete their regularly scheduled study evaluations. Study staff will target a 95% retention of enrolled participants over the 56 day follow-up period.

11.4. Summary of Primary and Secondary Objectives

For all analyses, all continuous titer measures will be log transformed unless otherwise specified

Analysis of Primary Objectives

In Section 4.1, we have described a way to equally assign enrolled siblings into two arms. By doing this, ignoring the possible nonindependence in siblings when obtaining group difference should still provide a consistent estimate of the group difference. The precision (i.e., the width of the 95% confidence interval) of the estimate may be inflated, while the degree of inflation of the precision depends on the number of co-enrolled siblings, which is not predictable at this stage. Given the fact that this study is a pilot study, we believe in the value of obtaining an accurate group difference estimate, and allow some leeway in precision. More precise estimates and more power could be achieved through future larger studies.

To assess the vaccine-induced and total antibody (IgG and IgA) response and IgA/IgG plus IgA/IgM ratios in the sera at days 28 and 56.

The serum antibody response described by the proportion of 4X increases or conversion from undetectable to detectable response in virus-specific antibody after two immunizations in intervention and control groups will be estimated and 95% confidence interval will be described for both groups, overall and by stratum. The proportion difference with 95% confidence interval will be reported, overall and by stratum. Due to possible variation in virus strains and the influenza virus vaccine formula in different flu seasons, analyses by season will also be described. Continuous titer values in both groups, overall or by stratum, will also be described and compared with point estimate along with 95% confidence intervals.

Titer ratios, such as IgA/IgG and IgA/IgM will be summarized with descriptive statistics, including mean, standard deviation, median and range, for each intervention group, overall or by season. Two-sample tests (t-test or Wilcoxon rank-sum test) will be applied whenever appropriate.

We will also apply generalized estimating equations (GEE) or mixed models to explore titer levels longitudinally.

As sensitivity analysis, similar analytic procedures will be additionally implemented by treating 4X increases or conversion from undetectable to detectable response in virus-specific antibody after two immunizations as an endpoint.

Analysis of Secondary Objectives

To assess the functional antibody response toward the influenza virus vaccine in the sera

Secondary analyses will examine sero-conversion defined as antibody HAI titers of $<1:20$ converting to $\geq 1:20$, or a four-fold increase in titer for participants with a starting titer of $\geq 1:20$. Sero-conversion rate will be estimated with proportion and 95% confidence interval for both groups, overall and by stratum. The rate difference will be described with point estimate and 95% confidence interval, overall and by stratum. Due to possible variation in virus strains and influenza virus vaccine compositions in different flu seasons, analyses by season will also be described.

Continuous titer values in both groups, overall or by stratum, will also be described and compared with point estimate along with 95% confidence intervals.

We will also apply generalized estimating equations (GEE) or mixed models to explore titer levels longitudinally.

Analysis of Exploratory Objectives

To describe the socio-demographic characteristics and nutritional diet among children participating in the trial.

Socio-demographic and dietary intake will be described with tables and descriptive statistics (frequency, proportion mean, standard deviation, median, range, etc...). The anticipated socio-demographic heterogeneity of participants may preclude further analysis, but if feasible, relationships between socio-demographic characteristics and dietary intake with outcomes will be examined.

To assess the feasibility of the food diary among healthy volunteers as measured by completion of the diary.

To assess the feasibility of the food diary among healthy volunteers, the proportion and 95% confidence interval of participants who complete and return the food diary will be calculated overall and at each visit time point.

To monitor serum Vitamin A and D levels at various time points.

Serum Vitamin A and D levels at screening, days 0, 28 and 56 will be monitored, plotted and described at each time point. Summary statistics, such as mean, standard deviation, median and range, will be provided for all time points. If feasible, paired comparisons and longitudinal modeling will be explored.

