4.0 TREATMENT PLAN

4.1. Treatment

This is a single site, pilot, randomized controlled trial in healthy children. The primary and secondary endpoints assessing vaccine-induced and total antibody (IgG and IgA) response and IgA/IgG plus IgA/IgM ratios in the sera as well as the functional antibody response toward influenza virus vaccine in the sera will be measured at Day 28, and 56. Approximately 100 total and 80 evaluable participants will be enrolled equally into two groups over 2 flu seasons, one of which will receive oral vitamins A and D (intervention), while the other group will receive the influenza virus vaccine and placebo gummy (control).

Potential participants will be approached by study staff. Participants who wish to participate in the study will complete the informed consent process prior to conducting the screening evaluations.

Allocation will be stratified by levels of Vitamin A using the surrogate retinol-binding protein (RBP). Vitamin A insufficiency (inclusive of deficiency) will be defined as $\leq 1.05 \mu\text{M}$ or $<22,000 \text{ ng/ml}$ RBP. RBP will be used to stratify participants based on previous mouse and human study demonstrating that vitamin A (for which RBP is a surrogate) is well correlated with IgA. RBP measurements are variable in humans, distributed somewhat equally above and below sufficiency cut-off. In contrast, our clinical work has indicated that study participants in Memphis are largely homogenous for vitamin D measurements in that most of the serum values fall below the sufficiency cut off. After the screening evaluations are obtained, the participant without co-enrolled siblings will be allocated to the intervention or placebo arm , in the pharmacy department, by means of a computerized stratified permuted block method (block size 4: allocation ratio 1:1) provided by the department of biostatistics. Co-enrolled siblings will first be stratified by their screening RBP levels, and then siblings within the same RBP level stratum will be equally assigned to intervention or control to avoid the chance of treatment imbalance, with the use of a computerized stratified permuted block method (block size 2: allocation ratio 1:1).

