11.2. Sample Size

The primary goal of the study is to estimate the effect size of vaccination when incorporating vitamin A/D supplements and standard care. The primary endpoint of interest will be the proportion of 4X increases or conversion from an undetectable to a detectable response in virus-specific antibody after two immunizations (compared to the starting titer) in intervention and control groups. We plan to enroll 40 participants per group in total. Assuming an attrition rate of about 5%, approximately 38 vaccine plus vitamin and 38 vaccine plus placebo participants will provide data for the primary objectives. Because this is a pilot study and there is very limited information about vitamin supplementation with influenza vaccination among children, the sample size was chosen based on past experience with clinical trials of other respiratory virus vaccines among a pediatric population at SJCRH and published literature (39). The sample size proposed will suffice for capturing the response rate difference between groups with a power of over 80% at a significance level of 5%, if the true average response rate overall with the Vitamin A/D supplements is over 62% (EAST 6) while the response rate in the vaccine only group is 30% on average, the majority of the enrolled participants are either vitamin A or D or both deficient as suggested by our experience. If the effect size is smaller, we still believe the estimated effect size with the proposed 80 participants will inform future larger studies.

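### The 95% interval for the primary response-rate difference takes no account of siblings being split across arms, so it is wider than the design warrants if siblings respond alike

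*Combined protocol and SAP*

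**What the plan says.** Section 4.1 stratifies co-enrolled siblings by screening RBP and then allocates them in blocks of two: "siblings within the same RBP level stratum will be equally assigned to intervention or control to avoid the chance of treatment imbalance". Siblings who fall in different RBP strata are not forced apart.

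Section 11.4 recalls this allocation, without the same-stratum condition, and reasons that "ignoring the possible nonindependence in siblings when obtaining group difference should still provide a consistent estimate of the group difference". It acknowledges a cost: "The precision (i.e., the width of the 95% confidence interval) of the estimate may be inflated", by an amount that depends on how many siblings enrol, which it calls unpredictable. It accepts that cost: "Given the fact that this study is a pilot study, we believe in the value of obtaining an accurate group difference estimate". Better precision and more power are left to later, larger trials.

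For the primary endpoint, "The proportion difference with 95% confidence interval will be reported, overall and by stratum". For titers, "Continuous titer values in both groups, overall or by stratum, will also be described and compared with point estimate along with 95% confidence intervals". For secondary seroconversion, "The rate difference will be described with point estimate and 95% confidence interval, overall and by stratum". No interval formula is named for any of these, and no adjustment for family. GEE or mixed models appear only as exploratory longitudinal analyses of titers, with no mention of family as a cluster.

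Section 11.2 sets the purpose: "The primary goal of the study is to estimate the effect size of vaccination when incorporating vitamin A/D supplements and standard care".

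**The concern.** Splitting siblings across arms is a form of matching. When matched children tend to respond alike, part of the between-family variation cancels in the difference between arms. An interval that treats all children as independent does not credit this cancellation, so it overstates the uncertainty.

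The effect-size estimate and its interval are the trial's main product and are meant to inform larger studies. Section 11.4 treats the lost precision as recoverable only in those studies, although part of it can be recovered from this trial's own data. Its stated reason, an unknown sibling count, is no obstacle: a family-clustered standard error uses whatever sibling sets turn up.

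**Working it through.** **Inputs from Section 11.2.** 38 evaluable children per arm (40 less about 5%); response 62% with vitamins and 30% without; 5% significance, taken as two-sided to match the 95% interval.

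**Assumptions, not in the documents.** The number of split sibling pairs, *k*, is set at 4, 10 or 19 (19 pairs is 38 of the 76 children). The within-pair response correlation, rho, is set at 0.1 to 0.5.

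**The plan's power figure.** The pooled response is 0.46.
- Null SE = sqrt(2 × 0.46 × 0.54 / 38) = 0.1143
- Alternative SE = sqrt((0.62 × 0.38 + 0.30 × 0.70) / 38) = 0.1083
- Power = Phi((0.32 − 1.96 × 0.1143) / 0.1083) = 81.2%

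This reproduces the stated power above 80%.

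**Independent-sample interval.** V = (0.2356 + 0.2100) / 38 = 0.01173, so the half-width is 1.96 × sqrt(V) = 21.2 percentage points.

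**With *k* split pairs.** Each pair contributes a positive covariance between the two arm proportions, which is subtracted from the variance of their difference:

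V_true = V − 2 × k × rho × sqrt(0.2356 × 0.2100) / 38²

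For k = 10 and rho = 0.3: V_true = 0.01173 − 2 × 10 × 0.3 × 0.2224 / 1444 = 0.01080. The half-width is 20.4 points, and the independent interval is too wide by a factor sqrt(0.01173 / 0.01080) = 1.042.

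The largest correlation possible with these rates is (0.30 − 0.62 × 0.30) / 0.2224 = 0.51, so rho = 0.5 is near the ceiling.

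| Split pairs | Too wide, rho 0.1 | Too wide, rho 0.3 | Too wide, rho 0.5 | Correct half-width, rho 0.3 | Large-sample coverage, rho 0.3 |
|---|---|---|---|---|---|
| 4 | 0.5% | 1.6% | 2.7% | 20.9 | 95.4% |
| 10 | 1.3% | 4.2% | 7.3% | 20.4 | 95.9% |
| 19 | 2.6% | 8.4% | 15.4% | 19.6 | 96.7% |

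**Siblings in different strata.** These can land in the same arm, which pushes the other way. Assume a 50/50 RBP split and a correlation phi between siblings' RBP status. A share 0.5 × (1 − phi) of pairs then straddles strata, and half of those share an arm. Enumerating the allocations at rho 0.3, for 4, 10 and 19 pairs:
- phi = 0: mean excess width 0.8%, 2.1% and 4.0%. The interval is more than 1% too narrow in 0.4%, 0.4% and 0.2% of allocations.
- phi = 0.5: mean excess width 1.2%, 3.1% and 6.2%. The interval is more than 1% too narrow in at most 0.02% of allocations.

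**Simulation.** The plain Wald interval was compared with a family-clustered interval using the CR2 small-sample correction and Satterthwaite degrees of freedom. There were 38 children per arm, all pairs were split, the binary correlation was about 0.29, the null was 46% in both arms, and each cell had 100,000 replicates.

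| Split pairs | Wald coverage | Mean half-width, Wald / CR2 | Null rejection, Wald / CR2 | Power, Wald / CR2 |
|---|---|---|---|---|
| 0 | 94.6% | 20.9 / 21.6 | not shown | not shown |
| 4 | 94.8% | 20.9 / 21.3 | 4.8% / 4.8% | 82.0% / 82.0% |
| 10 | 95.5% | 20.9 / 20.8 | 3.9% / 4.7% | 82.6% / 84.1% |
| 19 | 96.3% | 20.9 / 20.1 | 3.2% / 4.9% | 83.5% / 86.7% |

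CR2 coverage was 94.6% to 95.1% throughout. A separate simulation of split pairs gave a mean estimated difference of 0.320 in every setting, so the point estimate is unbiased.

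For normal log-titers at correlation 0.3 with 4, 10 and 19 split pairs, the t-test rejected a true null 4.7%, 4.1% and 3.3% of the time, against 5.1%, 4.9% and 4.8% for CR2. The CR2 half-width was 1.4%, 3.6% and 7.0% narrower.

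**The case against.** The strongest reply is that Section 11.4 already raises the issue, names the direction and the driver, and accepts a conservative trade-off for a pilot. That is true, and it rules out calling this a hidden error. It does not settle the matter, because the reason given (an unpredictable sibling count) does not prevent a clustered analysis, and the precision need not wait for a larger study.

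Three further points stand as limits on the weight:

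- **Size is assumed.** The effect could be zero if no siblings enrol. Nothing in the documents supports 19 pairs or a correlation near 0.5.
- **At low counts the planned interval is not conservative in practice.** Simulated Wald coverage is 94.8% at 4 pairs because ordinary small-sample undercoverage offsets the excess width, and it stays within about half a point of 95% up to 10 pairs. The remedy is also wider than Wald there (21.3 against 20.9 points at 4 pairs). Interpolating between 4 and 10 pairs, the two break even near 9.
- **Straddling shrinks the gain.** With independent sibling RBP status, power for Wald against CR2 is 81.7% and 81.6%, 82.2% and 82.7%, and 82.7% and 83.8% at 4, 10 and 19 pairs. Section 4.1 describes RBP as spread fairly evenly around the cut-off, so straddling is plausible.

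These points make the gain modest. They do not make ignoring the family structure the better choice: the clustered interval held close to nominal coverage at every sibling count tried and reflects same-arm as well as split siblings.

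**Conclusion.** The concern holds. If siblings' responses are positively correlated, the planned interval for the primary difference is wider than the split-sibling allocation warrants, and the same gap affects the seroconversion difference and the titer comparisons.

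At rho 0.3 with all pairs split, the precision discarded is worth about 38 × (V / V_true − 1) = 38 × 0.086, or roughly 3 extra children per arm with 10 pairs, and 38 × 0.176, or 6 to 7, with 19. The gain from correcting it is nil at 4 pairs and modest from about 10. A materially too-narrow interval is unlikely. The point estimate and the power statement are unaffected.

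Confidence is high on the mechanism and direction. The size rests on an assumed sibling count, response correlation and RBP correlation. This is a change worth making because it is cheap; the trial's validity does not depend on it.

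**What to change.** In Section 11.4:

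- Keep the unadjusted proportion difference as the estimate. Compute its 95% interval with a family-clustered robust standard error, counting children without siblings as clusters of one, and a small-sample correction such as CR2 with Satterthwaite degrees of freedom.
- Do the same for the secondary seroconversion difference and the log-titer mean differences, overall and by stratum. With an assumed 19 children per arm in a stratum and 0 to 9 split pairs, simulated CR2 coverage was 94.7% to 96.0%.
- Keep the independent-sample interval as a sensitivity analysis.
- Report the number of sibling sets by stratum and arm.
- If an estimate adjusted for RBP stratum is wanted, label it as a separate adjusted estimate. Family random effects in the exploratory longitudinal models are optional.

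The cost is SAP wording and slightly more analysis work. Sibling status is already needed for randomisation, and no extra children or samples are required. The drawback is a slightly wider interval than plain Wald if few siblings enrol: 21.6 against 20.9 points with no pairs.

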Current guidelines are based on the fact that many children younger than 9 years of age have not been infected with influenza viruses previously, and a booster dose is needed for them to produce a protective immune response (36). Previous research among healthy children has also demonstrated the efficacy of two doses of influenza vaccine in preventing laboratory-confirmed cases of influenza illness (37-38). Based on previous evidence and the current guidelines supporting the administration of two doses of influenza vaccine among young children, this study will require two doses of influenza virus vaccine for all participants.

Rationale for Vitamin A and Vitamin D Dose

Consistent with previous literature and our pre-clinical data (as detailed above), high dose vitamin supplementation will be utilized as part of this study (20,000 IU per dose of vitamin A and 2,000 IU per dose of vitamin D). A dose that is 10 times the recommended daily allowance (RDA) at the tolerable upper intake level (UL) will be used for vitamin A. The chosen vitamin A dose is unlikely to cause adverse effects as it is well below that recommended by the WHO for children in developing countries. According to UNICEF's guidelines "the World Health Organization (WHO) has established dosage guidelines; each child between 6 and 11 months is to receive 100,000 international units (IU) of vitamin A. This increases to 200,000 IU every six months from 12 to 59 months of age" (40). Vitamin D levels will be maintained at the UL (41), because although high-dose vitamin D has been successfully studied in humans, and a combination of vitamin A and D supplements support IgA production in research animals deficient in both vitamins, the correlation between vitamin D and IgA is not convincing in our human study. In addition, high-dose vitamin D can yield paradoxical effects, and vitamins A and D can act as antagonists to one another (42-44)

Additionally, we have conducted vitamin studies in vitamin A deficient mice (VAD) and in mice deficient for both vitamins A and D (VAD+VDD). Caveats to the direct translation of results from these mice to humans are: (i) the vitamin A content of a normal mouse diet is approximately 15X the RDA of humans based

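### The primary response-rate difference is planned as a crude difference; adjusting it for the starting titer, which is already collected, would be a free gain in precision (an efficiency point, not an error)

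*Combined protocol and SAP*

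**What the plan says.** Section 11.2 (Sample Size) makes effect-size estimation the primary goal. Its endpoint is the proportion with a 4X rise or "conversion from an undetectable to a detectable response in virus-specific antibody after two immunizations (compared to the starting titer"). The sample is said to detect the difference between arms "with a power of over 80% at a significance level of 5" percent. For the vitamin arm this assumes a rate above 62%; for control the text reads "while the response rate in the vaccine only group is 30% on average". On numbers, "approximately 38 vaccine plus vitamin and 38 vaccine plus placebo participants will provide data for the primary objectives".

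Section 11.4 (Analysis of Primary Objectives) gives the comparison: "The proportion difference with 95% confidence interval will be reported, overall and by stratum". It also describes results by season. It names no covariate for this comparison. The GEE or mixed models in the same section are exploratory, address titer levels and list no covariates.

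The stratum is screening RBP (protocol summary and Section 4.1). Serum for immunologic studies is scheduled before the first dose for every child: at screening (Sections 4.1, 6.1, 6.5) and again on Day 0 (Section 6.2, Appendix I).

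On prior immunity, Section 2.2 notes that "many children younger than 9 years of age have not been infected with influenza viruses previously". Section 3.2 excludes earlier receipt of the current season's vaccine, but not vaccination in previous seasons.

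**The concern.** The starting titer decides which rule a child must meet. A child who starts undetectable needs only to become detectable; a child who starts detectable needs a four-fold rise. Ages 2 to 8 are likely to mix children with and without earlier exposure, so response rates may differ between the two starting groups.

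If they do, and one arm happens to receive more undetectable starters, the crude difference moves for a reason unrelated to the vitamins. Randomisation does not stratify on titer, and at about 38 per arm such imbalances are common. The estimated difference is the pilot's main product and is meant to inform larger studies, so avoidable noise in it matters. The data needed to remove that noise are already in the schedule.

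**Working it through.** **Inputs from Section 11.2:** 30% (control), 62% (vitamin), 38 per arm, 5% significance. Sidedness is not stated; two-sided is assumed because 95% intervals are planned.

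**1. The plan's own power.** Mean rate = (0.30 + 0.62)/2 = 0.46.
- Null SE (pooled) = sqrt(2 × 0.46 × 0.54 / 38) = 0.1143.
- Alternative SE = sqrt((0.30 × 0.70 + 0.62 × 0.38)/38) = 0.1083.
- Power = Φ((0.32 − 1.96 × 0.1143)/0.1083) = Φ(0.885) = 81.2%.

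This agrees with the plan's figure of over 80%. The unpooled formula gives 84.0%.

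**2. Chance imbalance in starting titer.** Assume half the children start detectable. The SD of the between-arm difference in that share is sqrt(2 × 0.25/38) = 0.115, or 11.5 points. In simulation the difference is 10 points or more in 42% of trials and 20 points or more in about 8%.

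The shift in the crude difference is the imbalance times the response gap, where the gap is the response rate in undetectable starters minus that in detectable starters. A 10-point imbalance moves the estimate by 2 points at a gap of 20 and by 4 points at a gap of 40. A 1-SD imbalance at a gap of 40 moves it by 0.115 × 0.40 = 4.6 points.

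**3. Gain from adjustment.** Neither the share detectable (q) nor the gap is in the documents, so both are varied with the overall rates held at 30% and 62%.
- Control response: detectable starters 0.30 − gap × (1 − q); undetectable starters, that plus the gap.
- Vitamin arm: 0.32 higher in both groups.
- Unadjusted analysis: pooled z test.
- Adjusted analysis: Cochran-Mantel-Haenszel test and Mantel-Haenszel risk difference, by starting-titer status.
- 40,000 simulated trials per setting, 38 per arm.

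Power, unadjusted → adjusted:

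| Gap (points) | q = 30% | q = 50% | q = 70% |
|---|---|---|---|
| 0 | 81.6% → 81.2% | 81.6% → 81.1% | 81.3% → 80.8% |
| 20 | 81.6% → 82.5% | 81.5% → 82.7% | 81.3% → 82.2% |
| 30 | 81.4% → 83.9% | 81.2% → 84.5% | 81.4% → 84.1% |
| 40 | 81.1% → 86.6% | 81.7% → 88.5% | 81.4% → 86.9% |
| 50 | not possible | 81.6% → 92.8% | 81.5% → 90.6% |

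Type I error stays near 5% for both methods. At a gap of 10, adjustment gains nothing for any q from 10% to 90%. With 80-90% detectable, a gap of 40 gains only 1.5-4 points. Reversing the sign of the gap is the same as swapping q and 1 − q, so the direction of the link does not matter to the gain.

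**4. The same gain in interval width** (q = 50%, 1.96 × simulated SD):
- Unadjusted: 1.96 × 0.108 = 21.2 points.
- Adjusted, gap 20: 1.96 × 0.106 = 20.8.
- Adjusted, gap 30: 1.96 × 0.104 = 20.4.
- Adjusted, gap 40: 1.96 × 0.099 = 19.4.

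At a gap of 40 the variance ratio (unadjusted to adjusted) is 1.15-1.20 over these values of q. That is worth 38 × 0.15 = 5.7 to 38 × 0.20 = 7.6, about 6 to 8 more children per arm.

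**The case against.** **The size of the link is unknown.** A reader might infer from Section 2.2 that starting titer must be a strong predictor of response. The documents do not show this. The section says that children without earlier infection need a booster to reach a protective response, which suggests they respond less well. That pulls against their easier response rule, so the two effects may partly cancel and leave a small gap. This stands, and it is why the result is a range that includes no gain. The 91-93% figures at a gap of 50 need an extreme split (for example, control response of 55% against 5% with half detectable) and should not be quoted as the expected benefit.

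**No error has been shown.** A reader might infer that the crude difference is biased, its interval invalid, or the stated power wrong. None of these follows. The crude difference is unbiased under randomisation, its 95% interval already allows for chance imbalance in starting titer, and the power reproduces. The starting titer is also not ignored, since it defines the endpoint; but defining response against baseline does not adjust the comparison between arms for baseline. Nor is titer necessarily left wholly unbalanced: Section 2.2 reports an association between RBP and neutralizing titers, of unstated strength, so stratifying on RBP may balance it in part.

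**This is a pilot.** A simple crude difference is a legitimate choice with about 76 children. Section 11.4 does accept some loss of precision, but only in relation to siblings. The estimation goal makes precision relevant even if power is secondary.

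**Missing samples.** Section 6.0 foresees tests not done as scheduled, so a starting titer is scheduled for every child but not guaranteed. Adjustment loses nobody further, however: without a starting titer a child has no primary endpoint either.

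**Conclusion.** The point holds as a free improvement in efficiency. The plan compares arms by a crude difference in proportions and leaves out a baseline value that determines each child's response rule, is already scheduled before dosing, and is not a randomisation factor.

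Adjustment costs up to about 0.5 point of power if starting titer is unrelated to response, and gains nothing at a gap of 10 points. It gains roughly 1 point at a gap of 20, about 3 at 30 and about 5 to 7 at 40 when 30-70% of children start detectable, and less outside that range. These figures rest on assumed gaps and shares, an equal 32-point effect in both starting groups, a two-sided 5% test and 38 evaluable per arm.

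**What to change.** In Section 11.4, keep the endpoint and the risk-difference scale. Pre-specify the overall difference as either of the following, with a 95% interval:
- a Mantel-Haenszel risk difference stratified by starting-titer status (undetectable or detectable); or
- a standardised risk difference (g-computation from a logistic model) with arm and starting-titer status, or log starting titer, as terms.

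Report the crude difference beside it. Pre-specifying the choice avoids deciding on adjustment after an imbalance has been seen.

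Two definitions are needed first:
- **Which sample is the starting titer.** Sections 4.1 and 6.5 list serum at screening but not Day 0. The protocol summary, Section 6.2 and Appendix I include Day 0.
- **Which titer is used.** It should be the starting titer of the same antibody on which the response is judged, since IgG and IgA are both measured and Section 11.4 anticipates strain variation.

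Do the same for HAI sero-conversion in the secondary analysis, using the split at 1:20 already defined there.

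The cost is a few sentences of SAP text, a few lines of code and one model term in about 76 children. No new data are required.

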1.0 OBJECTIVES

1.1. Primary Objective

To assess the vaccine-induced and total antibody (including IgG and IgA) response after influenza virus vaccine administration and IgA/IgG plus IgA/IgM ratios at 28 and 56 days in sera

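### Section 11.4 compares log titres and IgA/IgG and IgA/IgM ratios between arms with no covariate; ANCOVA would be more precise if starting and follow-up values correlate above about 0.2

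*Combined protocol and SAP*

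**What the plan says.** Section 11.4 log-transforms titres unless otherwise specified. Under the primary objective it then states: "Continuous titer values in both groups, overall or by stratum, will also be described and compared with point estimate along with 95% confidence intervals". The same sentence is repeated for the functional (HAI) titres under the secondary objective. Neither place names an estimator or a covariate.

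The IgA/IgG and IgA/IgM ratios are summarised with descriptive statistics, "including mean, standard deviation, median and range, for each intervention group, overall or by season", and then: "Two-sample tests (t-test or Wilcoxon rank-sum test) will be applied whenever appropriate". No breakdown of the ratios by RBP stratum is mentioned.

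RBP stratum (the stratification factor for allocation in Section 4.1) and season enter only as separate breakdowns. The starting titre enters only through the binary responder definitions. Section 11.2, for example, defines the primary endpoint as a response "after two immunizations (compared to the starting titer) in intervention and control groups". On longitudinal models, Section 11.4 says: "We will also apply generalized estimating equations (GEE) or mixed models to explore titer levels longitudinally". No model terms are listed, and the sentence covers titres, not ratios.

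**The concern.** Section 11.2 gives the main aim as estimating an effect size and expects the estimate to inform larger studies even if the effect is smaller than assumed. The width of the interval is therefore what the pilot delivers.

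The primary objective in Section 1.1 covers total antibody and closes with "administration and IgA/IgG plus IgA/IgM ratios at 28 and 56 days in sera". The fourfold-rise or conversion endpoint is defined only for virus-specific antibody. For total IgG, total IgA and the two ratios, the continuous comparison is the only contrast between arms.

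The protocol itself gives reasons to expect the covariates to be prognostic. Section 2.2 reports associations of RBP with IgA, IgA/IgM and neutralising titres. Section 4.1 stratifies on RBP because vitamin A correlates with IgA. Section 11.4 expects seasons to differ. Comparing arms overall without these variables leaves explainable variation in the error term.

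**Working it through.** **Inputs from the documents.** 40 per arm, 5% attrition, response rates 62% and 30%, 5% significance (Section 11.2); 1:1 allocation stratified by two RBP levels (Section 4.1); two seasons (Section 11.3); immune responses measured in screening serum (Section 6.5). Two-sided testing is assumed because sidedness is not stated.

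**The plan's own figure.** 40 × 0.95 = 38 per arm. With the pooled z-test, the null standard error is √(2 × 0.46 × 0.54/38) = 0.1143 and the alternative one is √((0.62 × 0.38 + 0.30 × 0.70)/38) = 0.1083. Power = Φ((0.32 − 1.96 × 0.1143)/0.1083) = 81.2%, so the claim of over 80% reproduces. It concerns the binary endpoint, which this point leaves alone.

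**Width of ANCOVA relative to the unadjusted interval.** N = 76 and q = 3 covariate degrees of freedom (starting value, RBP stratum, season). Stratum and season are assumed to explain nothing beyond the starting value.

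ratio = √[(1 − r²)(1 + q/(N − q − 3))] × t(0.975, 71)/t(0.975, 74)

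The inflation term is 1 + 3/70 = 1.0429 and the t ratio is 1.9939/1.9925. At r = 0.5 this gives √(0.75 × 1.0429) × 1.0007 = 0.885. Equivalent unadjusted size per arm is 38/ratio².

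| r (assumed) | ANCOVA / unadjusted width | Equivalent n per arm |
|---|---|---|
| 0 | 1.022 | 36 |
| 0.2 | 1.001 | 38 |
| 0.3 | 0.975 | 40 |
| 0.5 | 0.885 | 49 |
| 0.7 | 0.730 | 71 |

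**Break-even.** Setting the ratio to 1 gives r² = 1 − (1.9925/1.9939)²/1.0429 = 0.042, so r = 0.206, or about 4% of variance explained. It is 0.200 at N = 80 and 0.178 at N = 100. With the starting value as the only covariate it is 0.119 at N = 76. Simulation with RBP exactly balanced across arms puts the three-covariate break-even near 0.17.

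**Simulation** (76 children, arm effect 0.5 SD, 2,000-4,000 runs per cell). The ranges span RBP balanced and unbalanced across arms, and the floor runs also span vaccine rises of 1 and 2 SD (2 SD in the unbalanced case only). With no floor and RBP balanced, the mean half-width falls from 0.455 SD to 0.441, 0.400 and 0.330 SD at r = 0.3, 0.5 and 0.7. Coverage is 94.6-95.6% for ANCOVA and 94.4-95.6% unadjusted, so both are valid.

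A detection floor is plausible for virus-specific titres, since Section 2.2 says "many children younger than 9 years of age have not been infected with influenza viruses previously". Change in width, ANCOVA against unadjusted:

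| Starting values undetectable | r = 0.3 | r = 0.5 | r = 0.7 |
|---|---|---|---|
| None (total Ig, ratios) | −2.4 to −3.1% | −11.5 to −12.2% | −27.3 to −27.5% |
| 30% | −2.0 to −2.7% | −9.5 to −10.3% | −22.6 to −24.0% |
| 50% | −1.3 to −2.0% | −7.8 to −8.8% | −18.6 to −20.4% |
| 70% | −0.3 to −1.2% | −5.4 to −6.8% | −13.5 to −16.3% |

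With no prognostic covariate the interval is 1.4% (balanced) to 2.2% (unbalanced) wider.

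**Against change scores.** The plan does not say whether the compared titres are follow-up values or changes. With no floor, ANCOVA is 18%, 12% and 6% narrower than an unadjusted change score at r = 0.3, 0.5 and 0.7. With a 50% floor the difference runs from −5.8% to +2.1% over that range of r, and with a 70% floor from −2.5% to +2.1%. An undetectable-at-baseline indicator brings the worst case at 70% to +1.3%.

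**The case against.** The strongest reply is that nothing here is an error. The unadjusted analysis is unbiased, the primary endpoint is binary and already uses the starting titre, and this is a pilot that explicitly tolerates some loss of precision. The size of the gain rests on a correlation the documents do not give: the figure of about 71 per arm needs r = 0.7 and no floor, while at r = 0.3 the gain is two children per arm. The titre sentence names no estimator, so it is underspecified rather than committed to an unadjusted analysis. For the ratios no confidence interval is planned at all. A longitudinal model with a suitable baseline term could recover much the same precision. The calculations treat all 76 children as independent, although siblings may co-enrol.

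Much of this stands as a limit on size. The gain is conditional, for ratios it applies to the interval implied by the t-test, and the percentages would shift if many siblings enrol. It does not remove the point. The tolerance for imprecision in Section 11.4 concerns sibling non-independence and is no reason to forgo precision that needs no new data. The longitudinal models are exploratory, state no terms and leave out the ratios. Silence on the estimator also leaves the choice between follow-up values, change scores and model terms open until the data are seen.

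**Conclusion.** The concern holds as a precision point, not a validity point. At 38 per arm the three-covariate ANCOVA breaks even at r of about 0.2. With no detection floor it narrows the interval by roughly 12% at r = 0.5 and 27% at r = 0.7. For virus-specific titres with 30-70% undetectable starting values, the gains are about 5-10% and 14-24% at those correlations. The downside against the unadjusted comparison is an interval about 2% wider.

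These figures assume r, independence between children, and no additional contribution from RBP stratum or season; any such contribution lowers the break-even. The case is firmest for total immunoglobulins and the ratios, where no vaccine-related floor is expected and there is no responder analysis. It is weakest for virus-specific titres if the team intended change scores and many children start undetectable.

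**What to change.** In Section 11.4, specify the overall Day 28 and Day 56 comparisons of log titres and log ratios as an ANCOVA on arm, log starting value, RBP stratum and season, reporting the adjusted difference with its 95% confidence interval. Use the same pre-vaccine sample as the responder endpoint and name it, because Section 6.5 lists screening serum while Section 6.2 also collects immunologic serum at Day 0. For virus-specific titres, add an undetectable-at-baseline indicator if many children start at the detection limit. List the same covariates in the GEE or mixed models. Keep the by-stratum and by-season results as descriptive, and leave the binary analyses unchanged.

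The cost is SAP wording; no visit, assay or participant is added. One choice should be made openly: modelling log ratios gives the ratios a mean contrast on the log scale in place of the open choice between t-test and Wilcoxon. If the rank test is wanted, it can stay as a supporting analysis.
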